6.2. Premature trial discontinuation

A patient can be withdrawn at any time from the study for the following reasons:

Patient's premature trial discontinuation could occur for the following reasons:

- Investigator's decision;
- An Adverse Event or an intercurrent condition that preclude continuation of treatment;
 - Specifically, an increase ≥ 3.0 x ULN in liver transaminases (AST/SGOT and/or ALT/SGPT) or an increase ≥ 2.0 x ULN in Alkaline phosphatase or in total bilirubin requires close observation with repeating liver enzymes and serum bilirubin tests two times weekly and clinical investigation to understand the etiology of this elevation. Frequency of retesting can decrease to once a month if abnormality stabilizes after this initial two weeks of follow-up and if the patient is asymptomatic. Discontinuation of the study treatment should occur if:
 - ALT or AST > 8 xULN
 - ALT or AST > 5 xULN for more than 2 weeks
 - ALT or AST > 3 xULN and total bilirubin > 2 xULN or INR >1.5
 - ALT or AST > 3 xULN with appearance of fatigue, nausea, vomiting, right upper quadrant pain or tenderness, fever, rash, and/or eosinophilia ($>5\%$).
- Worsening of the RA (according to physician evaluation);
- Major protocol violation;
- Withdrawal of consent;
- Administrative reasons from Sponsor.

A patient who prematurely exits the study will not be replaced.

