	
 ○ Specifically, an increase $\geq 3.0 \times$ ULN in liver transaminases (AST/SGOT and/or ALT/SGPT) or an increase $\geq 2.0 \times$ ULN in Alkaline phosphatase or in total bilirubin requires close observation with repeating liver enzymes and serum bilirubin tests two times weekly and clinical investigation to understand the etiology of this elevation. Frequency of retesting can decrease to once a month if abnormality stabilizes after this initial two weeks of follow-up and if the patient is asymptomatic. Discontinuation of the study treatment should occur if: 
 • ALT or AST $> 8 \times$ULN • ALT or AST $> 5 \times$ULN for more than 2 weeks • ALT or AST $> 3 \times$ULN and total bilirubin $> 2 \times$ULN or INR>1.5 • ALT or AST $> 3 \times$ULN with appearance of fatigue, nausea, vomiting, right upper quadrant pain or tenderness, fever, rash, and/or eosinophilia ($>5\%$). ▪ Worsening of the RA (according to physician evaluation); ▪ Major protocol violation; ▪ Withdrawal of consent; ▪ Administrative reasons from Sponsor.

Patient Follow-up
	
On Day 84 +/- 2 days, patients willing to carry on the study treatment will be able to take part in an open-label study (ABX464-302). In any other case, the subjects will exit the study (EOS) and will be treated according to the standard of care. The ABX464-302 follow-up study is a separate clinical study subject to health authorities and ethics committee approvals.

Data Safety Monitoring Board (DSMB)
	
A Data Safety Monitoring Board with expertise and experience in the management of Rheumatoid Arthritis will review the safety of the trial. The DSMB will meet after the first 6 patients (i.e. 50mg) are dosed for at least 2 Weeks to check the 50mg dose tolerability. Once the DSMB recommendation is granted, the next 6 patients will be randomized to receive either ABX464 50mg, ABX464 100mg or placebo. A second DSMB meeting will then be held when these 6 next patients are treated for at least 2 weeks, to check the 100mg dose tolerability and grant the recommendation to resume patient's randomization.
 
In addition, from the first DSMB onwards, meetings will be held every month during the study period.

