5.3.5. Hematology and biochemistry

For hematology and biochemistry panels, local laboratory will be used.

Each laboratory value that is outside of the institution's normal range will be identified. The Investigator will be responsible for assessing the clinical significance of laboratory abnormalities. If the Investigator is uncertain about the clinical significance of a laboratory abnormality, he/she will consult with the Sponsor medical monitor.

The Investigator should follow any clinically significant laboratory abnormalities until resolution.

The Table 1 displays the clinical laboratory parameters that must be measured.

Table 1: Laboratory Tests

HEMATOLOGY	BIOCHEMISTRY
Hemoglobin	Sodium
Hematocrit	Potassium
WBC	Chloride
Neutrophils	Calcium
Lymphocytes	Phosphate
Monocytes	Glucose
Eosinophils	BUN or urea
Basophils	Creatinine
Platelet count	AST / SGOT
ESR	ALT / SGPT
Prothrombin time and/or INR*	Alkaline phosphatase
Fibrinogen*	GLDH
	LDH
	Lipase
	Total cholesterol
	HDL cholesterol
	LDL cholesterol
	gGT
	Total bilirubin
	Total protein
	Albumin
	CRP
	T3, T4, TSH (for French sites only)
	Troponin I & T*

Tests of TB (Quantiferon TB Gold Plus), HIV (anti-HIV Ab), HCV (anti-HCV Ab), HBV (HBsAg, anti-HBs Ab), anti-HCV Ab, will be performed only at screening. * Except at Week 1 & 2

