5.3.8. Summary of blood samples

The table 2 below summarizes the volume of blood to be sampled at each study visit.

Table 2: Blood Volume

	REQUIRED VOLUME	COLLECTION TUBE	SCR D-30	BSL D0	D7	D14	D28	D56	D84	EOS D105	TOTAL
			SCR	BL	V1	V2	V3	V4	V5	EOS	
Hematology (Hemoglobin, Hematocrit, Red Cell Count, MCV, MCHC, Platelets, White cell count with diff.)	0.5mL EDTA blood	2mL EDTA tube	2	2	2	2	2	2	2	2	16
Prothrombin time/INR and fibrinogen		2,7 mL plasma Citrate	2,7	2,7			2,7	2,7	2,7	2,7	16,2
ESR	1mL EDTA blood	2mL EDTA tube	2	2	2	2	2	2	2		14
Biochemistry panel incl CRP, βHCG and thyroid function parameters (French sites only*)	2 mL serum + 2mL*	2 x 5mL serum gel tube	5 +5*	5 +5*	5 +5*	5 +5*	5 +5*	5 +5*	5 +5*	5 +5*	40 +40*
HBsAg, anti-HBs Ab, anti-HCV Ab, anti-HIV Ab	0.75 mL serum	2.5mL serum gel tube	2,5								2,5
Quantiferon TB Gold Plus	4 mL plasma	4 x 1mL tube	4								4
Cytokines determination on serum	min 6 mL serum	2 x 5mL serum gel tube		10	10	10	10	10	10	10	70
Cytokines determination on total blood		2 x 1 mL (Truculture® tube)		2				2			4
Samples for flow cytometry cells count **		4 x 6mL EDTA tube		24**				24**			48**
Paxgene® Tube (miR-124)	5 mL total blood	2 x 2,5 mL Paxgene® tube		5				5			10
PK samples	1.0 mL serum	2mL Li-heparin tube		6 (1,2, 3h post dose)		8 (pre-dose & 1,2, 3h post dose)		8 (pre-dose & 1,2, 3h post dose)		2 (trough levels)	24
Total per visit			18,2 +5*	34,7 +5* +24**	19 +5*	27 +5*	21,7 +5*	36,7 +5* +24**	21,7 +5*	21,7 +5*	200,7 +40* + 48**

*Only in French sites; **Only in French Coordinating Investigator Site

INVESTIGATIONAL PRODUCT(S)

All investigational products to be used in this study have been manufactured, packaged and labelled by contract manufacturers for ABIVAX, according to GMP standards and are supplied to investigators free of charge.

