5.6. Administration and Dosing

5.6.1. Administration of the investigational product

Following randomization, patients will be treated with a daily dose of either 50mg or 100mg ABX464 or will receive placebo.

Treatment groups:

Intervention/treatment Active Arm	
Group #1 (n=20): 100mg qd	2 capsules of 50mg ABX464
Group #2 (n=20): 50mg qd	1 capsule of 50mg ABX464 + 1 capsule of matching placebo
Group #3 (n=20): Placebo	2 capsules of matching Placebo

Patients will be orally dosed in a fed condition (regular breakfast) with a glass of water.

On Day 84 visit, the patient will not take the ABX464-301 study medication (last day of study medication will be on Day 83).

Patient enrolled in the ABX464-302 maintenance study will start the study medication on Day 84 (301 study)/D0 (302 study), ABX464 50mg once daily, right after the study visit.

A paper diary in which the patient should report the number of capsules taken and the intake time from baseline visit onwards, will be given to the patient at baseline.

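### INR > 1.5 is a liver stopping criterion, but the twice-weekly repeat tests after a liver flag do not include INR, and PT/INR is not scheduled at D7 or D14

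*Protocol*

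**What the plan says.** **Stopping rule.** Protocol 6.2 (Premature trial discontinuation) lists four liver criteria for discontinuing study treatment. One is "ALT or AST > 3 xULN and total bilirubin > 2 xULN or INR >1.5". The synopsis carries the same list.

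**Repeat testing.** Under 6.2, a transaminase value of at least 3.0 x ULN, or alkaline phosphatase or total bilirubin of at least 2.0 x ULN, "requires close observation with repeating liver enzymes and serum bilirubin tests two times weekly and clinical investigation to understand the etiology of this elevation". The synopsis likewise names "repeating liver enzymes and serum bilirubin tests two times weekly". Retesting may fall to monthly "if abnormality stabilizes after this initial two weeks of follow-up and if the patient is asymptomatic".

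**Scheduled coagulation tests.** Table 1 in Protocol 5.3.5 lists "Prothrombin time and/or INR" with an asterisk, and its footnote ends "will be performed only at screening. * Except at Week 1 & 2". SAP 9.2.1 repeats the table and the exception. In Table 2 (Protocol 5.3.8), the row for "Prothrombin time/INR and fibrinogen" has a 2.7 mL citrate tube at screening, baseline, D28, D56, D84 and EOS, and is blank at D7 and D14.

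**End of dosing.** Protocol 5.6.1 says the "last day of study medication will be on Day 83".

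**The concern.** A numeric stopping threshold works only if the protocol requires the measurement it depends on. Here the sponsor made INR an alternative to bilirubin, so it is meant to catch patients whom bilirubin would miss. Yet the tests that follow a flagged patient name only enzymes and bilirubin, and the two earliest on-treatment visits drop PT/INR.

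A site that follows the text could keep dosing a patient at, say, ALT 4 x ULN with bilirubin at or below 2 x ULN while one of the stated stopping criteria goes unmeasured. Flags near the threshold are foreseeable, because every patient takes methotrexate. Its product summary (Protocol Appendix 5, section 4.4) reports temporary transaminase rises to two or three times ULN in 13 to 20% of patients. That figure says nothing about how often INR would also be raised.

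**Working it through.** No power or sample-size calculation applies. The check is whether the schedule supplies the measurement that the stopping rule needs.

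**Step 1: reproduce Table 2.** If PT/INR were drawn at D7 or D14, the printed visit totals would have to include a 2.7 mL citrate tube.

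- D7: hematology 2 + ESR 2 + biochemistry 5 + serum cytokines 10 = 19 mL. Printed: 19.
- D14: 2 + 2 + 5 + 10 + PK 8 = 27 mL. Printed: 27.
- Citrate row: 6 draws x 2.7 = 16.2 mL. Printed: 16.2.
- All eight visit totals sum to 200.7 mL, as printed (base volumes, without the French-site additions).

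Table 2 and the Table 1 footnote therefore agree that no PT/INR is drawn at D7 or D14. The flow chart in 5.1 marks hematology and biochemistry at both visits, but the more specific tables remove PT/INR there.

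**Step 2: time to the next required PT/INR after an ALT/AST flag.** All visits have a window of ± 2 days.

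| Flag at | Next required PT/INR | Nominal gap | Range with windows |
|---|---|---|---|
| D7 | D28 | 28 − 7 = 21 days | 26 − 9 = 17 to 30 − 5 = 25 |
| D14 | D28 | 28 − 14 = 14 days | 26 − 16 = 10 to 30 − 12 = 18 |
| D28 | same day, then D56 | 27 dosing days between (D29 to D55) | – |
| D56 | same day, then D84 | 27 dosing days between (D57 to D83) | – |

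Dosing runs from D0 to D83, which is 84 daily doses. D7 to D27 covers 21 of them (25%), and D14 to D27 covers 14 (17%). After a D56 flag, the next required sample (D84) comes after the last dose.

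**Step 3: who falls in the gap.** Remove everyone the other liver criteria would stop. What remains is ALT/AST above 3 and up to 8 x ULN (and not above 5 x ULN for more than two weeks), total bilirubin at or below 2 x ULN, no listed symptom or eosinophilia, and no INR ordered during the etiology work-up. Within that group, the rule fails only for a patient whose INR exceeds 1.5.

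**Step 4: blood volume of adding INR.**

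- First two weeks: 2 x 2 = 4 repeats; 4 x 2.7 = 10.8 mL; 10.8 / 200.7 = 5.4% of the base volume.
- Upper case, a D7 abnormality that never stabilizes: (84 − 7) / 7 = 11 weeks; 11 x 2 = 22 repeats; 22 x 2.7 = 59.4 mL. If three of these fall on D28, D56 and D84, where a citrate tube is already drawn, the addition is 19 x 2.7 = 51.3 mL.

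**The case against.** The strongest reply is that the repeat sentence is not meant as a complete list. It also requires close observation and a clinical work-up of the cause, and an investigator applying the stopping list has good reason to order an INR. Eosinophils appear in the next criterion and are not in the repeat panel either. This has force, but the work-up permits an INR and does not require one. Eosinophils are at least measured at every scheduled visit, including D7 and D14; PT/INR is not.

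There are other safeguards. Entry requires ALT, AST, alkaline phosphatase and bilirubin below 1.5 x ULN (4.2.1). Clinically relevant hepatic abnormality is excluded (4.2.2). Warfarin is prohibited (5.12.3). Significant laboratory abnormalities are followed to resolution (5.3.5). The DSMB meets monthly (3.1.3), and the investigator may stop treatment at any time. None of these mandates an INR, but together they reduce the consequence, and that part of the objection stands.

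A reader might go further and link the gap to the minipig findings in Protocol 1.2.5.1, where liver toxicity appeared near the end of the third month, and conclude that patients are exposed between D56 and D83. The documents do not support that. No laboratory tests are scheduled between D56 and D84, so an elevation first arising there would trigger no flag and no repeats, and adding INR to the repeats would not help. Nor does that timing point to Weeks 1 and 2, where the gap in scheduled PT/INR lies. The same section reports no hepatotoxicity signs in treated patients and gives the sponsor's view that they are not at increased risk.

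**Conclusion.** The point holds as a limited gap in the liver monitoring text. A stated stopping criterion depends on a test that the flag-triggered repeats do not require and that is not scheduled at D7 or D14. For an early ALT/AST flag, the next required PT/INR is 21 days (17 to 25) or 14 days (10 to 18) away. For a flag at D28 or D56, the first value is available the same day and only the interim follow-up is uncovered.

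The bilirubin and transaminase-level criteria can be applied from the repeat panel, and the symptom criterion does not need INR. It would be wrong to conclude that the liver stopping rules as a whole do not work or that flagged patients are unmonitored. The day counts are the longest intervals the text allows; any INR ordered in the work-up shortens them. No rate is claimed for the affected profile, because the documents give none.

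The conclusion assumes that INR > 1.5 is paired with ALT/AST > 3 x ULN, which is the natural reading of the criterion. The and/or wording leaves open that INR > 1.5 alone was intended. INR is needed under either reading, but the documents do not settle which is meant. Rewriting the criterion with brackets could narrow a safety stop, so this is a question for the sponsor.

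**What to change.** 1. In Protocol 6.2 and the synopsis, add INR to the repeat panel for an ALT/AST flag. Start with the first repeat draw and continue at each repeat while ALT/AST is at or above 3 x ULN.
2. Where Table 1 allows prothrombin time and/or INR, require INR itself to be reported. As worded, a site could report prothrombin time alone, which cannot be read directly against the 1.5 threshold.
3. Ask the sponsor to confirm whether INR > 1.5 is meant to be paired with ALT/AST > 3 x ULN. If INR alone was intended, repeats in flagged patients would not be enough, and PT/INR at D7 and D14 would need to be considered. That would raise those visits to 21.7 and 29.7 mL and the base total to 200.7 + 5.4 = 206.1 mL.

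The cost of items 1 and 2 is protocol wording plus one 2.7 mL citrate tube at repeat draws that already take place: 10.8 mL over the first four, and up to about 59 mL if a D7 abnormality never stabilizes. No visit is added, and the thresholds, sample size and power do not change.

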3.1.3. Data Safety Monitoring Board

An independent Data Safety Monitoring Board (DSMB), with expertise and experience in the pathology, and without direct involvement in the conduct of the trial, will be set up specifically to guarantee effective protection of patients, ensure the ethical conduct of the trial, benefit/risk ratio of the trial, and to ensure the independent review of the scientific results during the trial and at the end of the trial. Besides, the DSMB may recommend the early termination of the trial at any time if an unacceptable toxicity occurs.

The DSMB will meet after the first 6 patients are dosed (50mg or matching placebo) for at least 2 weeks to check the 50mg dose tolerability. Once the DSMB recommendation is granted, the next 6 patients will be randomized to receive either ABX464 50mg, ABX464 100mg or placebo.

A second DSMB meeting will then be held when these 6 next patients are treated for at least 2 weeks, to check the 100mg dose tolerability and grant the recommendation to resume patient's randomization.

In addition, from the first DSMB onwards, meetings will be held every month during the study period. The DSMB will also review all potential causally-related Serious Adverse Events within 7 days of the initial report.

The DSMB has only a consultative role. It will inform the Sponsor who will decide whether the DSMB recommendation will be followed. A DSMB charter must be available upon submission of the trial (initial protocol) to the respective competent authorities.

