5. STUDY ASSESSMENTS AND PROCEDURES

5.1. Study Flow Chart

A detailed study flow chart (with all assessments) is displayed hereafter.

	Screening Period	Study Treatment Period						Follow-up Period
	D-30 to D-1	D0	D7	D14	D28	D56	D84	D105
		W0	W1	W2	W4	W8	W12	W15
Time Window (time between two visits ≤ 30 days)			± 2 days	± 2 days	± 2 days	± 2 days	± 2 days	± 2 days
	Screening	Baseline	V1	V2	V3	V4	V5	EOS
Obtained Informed Consent	X							
Check of IN/EX Criteria	X							
Medical History	X							
Height Measurement (cm)	X							
Body Weight (kg)	X	X	X	X	X	X	X	X
Physical Examination	X	X	X	X	X	X	X	X
Vital signs	X	X	X	X	X	X	X	X
Concomitant Medications	X	X	X	X	X	X	X	X
ECG (12 lead)	X	X					X	X*
Blood Pregnancy test (WOCBP)	X				X	X	X	X
Urine Pregnancy test (WOCBP)		X						
Randomization		X						
ABX464/placebo treatment dispensation		X			X	X		
Hematology + Biochemistry#	X#	X	X	X	X	X	X	X
Blood samples drug PK (pre-dose)				X		X		X**
Blood samples drug PK (1-, 2- & 3- hours post-dose)		X		X		X		
Blood samples for Cytokines (gel tube)		X	X	X	X	X	X	
Blood samples for Cytokines (Truculture® tube)		X				X		
Blood samples for flow cytometry cells count***		X				X		
Blood samples for CRP, ESR	X	X	X	X	X	X	X	
Blood samples for miR-124 (Paxgene® tube)		X				X		
Tender Joint Count (28)	X	X		X	X	X	X	
Swollen Joint Count (28)	X	X		X	X	X	X	
Patient Global Assessment of Disease (PtGA-VAS)	X	X		X	X	X	X	
Patient assessment of Joint Pain (Pain-VAS)		X		X	X	X	X	
Investigator Global Assessment of Disease (PrGA-VAS)		X		X	X	X	X	
Health Assessment Questionnaire – Disease Index (HAQ-DI)		X		X	X	X	X	
Functional Assessment of Chronic Illness Therapy (FACIT)-Fatigue		X		X	X	X	X	
Patient diary (dispensation/check)		X	X	X	X	X	X	
Adverse Events recording	X	X	X	X	X	X	X	X
Follow-up Headache Questionnaire in case of persistent headache (see section 5.3.2)			X (throughout the study, if needed)					
Dermatologist consultation in case of skin effect (see section 5.3.2)			X (throughout the study, if needed)					

#Tests of TB, HIV, HCV, HBV only at screening; *ECG at EOS visit in case of early termination only; **trough levels PK samples; ***Only in French Coordinating Investigator's Site; Two visits should not be conducted more than 30 days apart

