6. PATIENT COMPLETION AND WITHDRAWAL

6.1. Patient Completion

Treatment with ABX464/Placebo shall continue up to Week 12/ Day 83, except if a patient fulfils a premature discontinuation criterion (defined below).

On Day 84, patient will not take ABX464-301 study medication.

On Day 84, patients willing to carry on the study treatment will be able to take part in the long-term maintenance study (ABX464-302). Patient will sign the ABX464-302 specific informed consent and will start ABX464-302 study drug administration (50mg once daily).

In any other case, patients will exit the study (EOS) and will be treated according to the standard of care. The ABX464-302 follow-up study is a separate clinical protocol subject to health authorities and ethics committee approvals.

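### The step-down to monthly liver retesting has no ALT/AST ceiling, so a patient who rises above 5×ULN after detection and is judged stable can reach the two-week stop criterion with no test required

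*Protocol*

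**What the plan says.** Section 6.2 of the protocol, worded alike in the synopsis, puts two rules in one paragraph.

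- **Retesting.** ALT or AST at or above 3×ULN calls for close observation, liver tests twice a week and "clinical investigation to understand the etiology of this elevation". Then: "Frequency of retesting can decrease to once a month if abnormality stabilizes after this initial two weeks of follow-up", if the patient is also asymptomatic. Stabilization is not defined, and no ALT/AST level bars the step-down.
- **Stopping.** Study drug should stop when ALT or AST is above 8×ULN; above 5× "ULN for more than 2 weeks"; above 3×ULN with bilirubin above 2×ULN or INR above 1.5; or above 3×ULN with listed symptoms or eosinophilia.

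Outside that paragraph, the flow chart in Section 5.1 schedules biochemistry on Days 7, 14, 28, 56 and 84 and adds that "Two visits should not be conducted more than 30 days apart". Section 5.3.5 says "The Investigator should follow any clinically significant laboratory abnormalities until resolution", without an interval. Section 3.1.3 says that "from the first DSMB onwards, meetings will be held every month during the study period". Section 1.2.5.1 states that a liver monitoring plan is in place, but the only liver retest rule in the protocol is the one above.

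**The concern.** The two rules run on different clocks. The two weeks of twice-weekly testing start at 3×ULN. The two weeks of the stop criterion start above 5×ULN. If the higher line is crossed some days after the lower one, the stop criterion matures after intensive testing may already have ended. A criterion based on duration can be applied only if a sample shows that the value is still raised, and the step-down lets that sample lapse.

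At stake is continued daily ABX464 past a stated liver threshold, with no result to show that it has been passed. Section 1.2.5.1 names the liver as a main target organ in animals, and Section 5.12.1 makes methotrexate mandatory for everyone.

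**Working it through.** The plan states no figure for this gap, so there is none to reproduce. The check is day arithmetic.

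**Inputs**
- T = day of the 3×ULN trigger, taken at a routine visit: 7, 14, 28 or 56 (Section 5.1).
- Twice-weekly samples to T+14, taken as T+3, T+7, T+10 and T+14. The exact days are an assumption.
- After T+14: routine visits on Days 28, 56 and 84, plus monthly retests 28 to 30 days after T+14.
- F = day of the first sample above 5×ULN. Base cases are F = T+3 and F = T+7, leaving 11 or 7 flat days before the step-down.

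**Formulas**
- Two-week mark: M = F + 14.
- Gap = N − M, where N is the first required sample on or after M.

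| T | F | M | N | Gap (days) |
|---|---|---|---|---|
| 7 | 10 | 24 | 28 | 4 |
| 7 | 14 | 28 | 28 | 0 (no gap) |
| 14 | 17 | 31 | 56 | 25 |
| 14 | 21 | 35 | 56 | 21 |
| 28 | 31 | 45 | 56 | 11 |
| 28 | 35 | 49 | 56 | 7 |
| 56 | 59 | 73 | 84 | 11 |
| 56 | 63 | 77 | 84 | 7 |

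The monthly retests fall on Days 49–51, 56–58, 70–72 and 98–100 for the four triggers. None comes before N in these cases. For T = 56, the Day 84 sample follows the end of dosing: "last day of study medication will be on Day 83".

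**Sensitivity**
- *Visit window.* With Week 8 at Day 54 to 58, the Day 14 trigger gives 54 − 35 = 19 to 58 − 31 = 27 days.
- *Later crossing.* For T = 14, F = T+10 gives 56 − 38 = 18 and F = T+14 gives 56 − 42 = 14, so the range over the full two weeks is 14 to 25 days. These cases leave only 4 or 0 flat days. For F = T+10 at the other triggers: T = 7 gives 49 − 31 = 18 to 51 − 31 = 20 days, or 56 − 31 = 25 if the Day 28 visit restarts the month; T = 28 gives 56 − 52 = 4; T = 56 gives 84 − 80 = 4.
- *Strict reading.* If a value at exactly 14 days does not count as more than two weeks, the single 0 becomes 49 − 28 = 21 to 51 − 28 = 23 days. The other seven base cases are unchanged.
- *Twice-weekly testing continued.* Samples at T+17 and T+21 fall on the mark, so the gap is 0 in all eight cases (3 to 4 days on the strict reading).

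**Patients.** The documents give no rate for such elevations. About 40 of the 60 patients receive ABX464. As pure assumptions, let 1% to 5% exceed 5×ULN, and let 10% to 50% of those meet every other condition. Then 40 × 0.01 × 0.10 = 0.04 to 40 × 0.05 × 0.50 = 1.0 patients.

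**The case against.** The best answer is that a patient found at 3×ULN who then climbs above 5×ULN within two weeks is worsening, not stable, so a sensible investigator would keep testing twice weekly. The step-down is optional. The stop rule sits just below it and still binds: under Section 6.1, treatment runs its course "except if a patient fulfils a premature discontinuation criterion". A site that knows the two-week limit is running can honor it only by retesting. The investigator may withdraw a patient at any time, and close observation, the etiology work-up, follow-up until resolution and monthly DSMB meetings all apply. Section 1.2.5.1 reports no hepatotoxicity in treated patients. The methotrexate SmPC in Appendix 5 (its Section 4.4) calls for stopping methotrexate when liver tests become abnormal, and for closer enzyme monitoring with other hepatotoxic products.

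Much of this stands, and it keeps the point small. It does not close the gap. The text neither requires nor excludes calling 7 to 11 flat days stable, and none of these safeguards sets a retest at the mark. The criteria for >8×ULN, bilirubin, INR and eosinophilia also need a blood sample, so a change in them would go unseen over the same interval. Only symptoms work without one.

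**Conclusion.** The point holds as a minor, cheaply mended weakness in a safety rule. It needs all of these: a crossing above 5×ULN after the trigger but inside the two weeks; an asymptomatic plateau at >5 to 8×ULN, with bilirubin and INR within their stop limits; and a site that judges this stable and uses the step-down. Given those, the size is 21 to 25 days after a Day 14 trigger with a crossing at 3 to 7 days, and 0 to 11 days after the other triggers. Few patients would be affected, and only those on active drug would have prolonged ABX464 exposure.

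A reader might infer more than the documents support:
- *That anyone above 5×ULN can slip through.* Patients already above it at the trigger have the two-week sample on their mark, so the point does not rest on them.
- *That gaps of three weeks or more are typical.* In the base cases only the Day 14 trigger exceeds 11 days. The longer Day 7 gaps need a later crossing or the strict reading.
- *That the protocol sets aside its own stop rule, or that this is a major defect.* The rule stays in force; what is missing is a required test at the moment it matures.

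**What to change.** In Section 6.2 and the synopsis:
- allow monthly retesting only once ALT and AST are both at or below 5×ULN;
- while either is above 5×ULN on study drug, continue twice-weekly tests;
- count the two weeks of the stop criterion from the first sample above 5×ULN.

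This takes two or three sentences. In the eight base cases it adds 1 to 2 local liver panels per affected patient up to the mark, and one more on the strict reading, so about 1 to 3. Testing after study drug has been stopped is a separate matter, and this point gives no ground for a new rule on it.
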